#### Gastric/Duodenum and Targeted Biopsy

Biopsy specimens from the stomach and/or duodenum will be obtained at visit 2 in all patients <18 years of age to rule out alternate etiologies of esophageal eosinophilia. Stomach and/or duodenal biopsies will be obtained in adults only in the event of abnormal endoscopic findings (other than typical EoE findings) or clinical suspicion of alternate etiologies. All randomized patients found to have stomach and/or duodenal abnormalities at baseline will have follow-up stomach and/or duodenal biopsies at week 24 and week 52.

### **4.4. Efficacy Variable**

#### **4.4.1. Primary Efficacy Variable (s)**

The co-primary endpoints for Part B are:

- Proportion of patients achieving peak esophageal intraepithelial eosinophil count (from all 3 regions) of  $\leq 6$  eos/hpf at week 24
- Absolute change in DSQ score from baseline to week 24

#### Peak esophageal intraepithelial eosinophil count

Peak esophageal intraepithelial eosinophil count will be measured from esophageal biopsies. A total of 9 mucosal pinch biopsies will be collected at each time point from 3 esophageal regions: 3 proximal, 3 mid, and 3 distal. Two samples from each region will be used for the histology and other tissue analyses. The third sample from each region will be processed for RNA analyses. The quantity of eosinophils in the most inflamed high power field (HPF) for each of the 3 esophageal regions (proximal, mid and distal) will be determined by a pathologist at a central pathology reading center who will be blinded to the treatment assignment. The peak esophageal intraepithelial eosinophil count at each visit is the maximum of the quantities of eosinophils in the most inflamed HPFs across the 3 regions. For example, if for a particular patient, at week 24, the quantity of eosinophils in the most inflamed HPF is 2/hpf, 3/hpf, and 4 /hpf from the proximal, mid, and distal regions, respectively, the peak eosinophil count will be considered as 4/hpf for week 24. If the quantity of eosinophils is missing for 1 or 2 esophageal regions, the peak eosinophil count will be the maximum of the quantities of eosinophils from the region(s) where eosinophil quantities are available. To participate in the study, patients must have a peak intraepithelial eosinophil count  $\geq 15$  eos/hpf (400 $\times$ ) in at least 2 of the 3 esophageal regions sampled.

Esophageal biopsies will be obtained by endoscopy at the second screening visit (visit 2), week 24 and week 52 (EOS) or ET visits. For patients who receive rescue treatment during Part B, the endoscopy/biopsy procedures should be performed prior to the initiation of rescue treatment; however, Protocol Amendment #4 allows for rescue treatment to be initiated if, due to the COVID-19, an endoscopy procedure can not occur. Patients undergoing endoscopy/biopsy due to the initiation of rescue will not undergo the scheduled endoscopy/biopsy at weeks 24 and 52.

Due to COVID-19 restrictions, patients may postpone the week 24 visit until an in-clinic visit can be done for biopsy. Data handling for the biopsy data from those delayed week 24 visits will be detailed in section 5.6.1.

### Dysphagia Symptom Questionnaire (DSQ) Score

The DSQ is a validated PRO that has been used in clinical studies to measure the frequency and intensity of dysphagia (Hudgens, 2017). For patients who respond “No” to question 1 (“Since you woke up this morning, did you eat solid food?”), a modification was made to the DSQ by asking a follow-up question to probe if patients avoided solid food due to their problems with swallowing solid food. The DSQ uses a daily recall period and will be completed by the patient daily using an eDiary from screening through end of study or ET visit.

The questions and scoring of DSQ are presented in the table below. Question 1 is a screening question; patients will proceed with the questionnaire depending on their response to question 1:

- If the response to question 1 is ‘No’, question 1a will be asked to collect reason for not eating solid food and the remaining items on the DSQ are not scored. Data for that day is considered to be missing for analysis but diary completion is considered compliant for that day.
- If the response to question 1 is ‘Yes’, patient will skip question 1a and move on to questions 2, 3 and 4. Only questions on the frequency (question 2) and severity (question 3) of dysphagia contribute to the total DSQ score. Although question 4 related to pain was included in the DSQ, pain was not highlighted as an important symptomatic factor based on interviews of adolescent and adult patients with EoE. Thus, question 4 was considered as a standalone item for exploratory analysis.

### **Dysphagia Symptom Questionnaire (DSQ) (Adapted from Hudgens, 2017)**

Question Number	Response Option	Score
1. Since you woke up this morning, did you eat solid food?	No	No score assigned
	Yes	No score assigned
[REDACTED]	[REDACTED]	[REDACTED]
	[REDACTED]	[REDACTED]
	[REDACTED]	[REDACTED]
	[REDACTED]	[REDACTED]
2. Since you woke up this morning, has food gone down slowly or been stuck in your throat?	No	0
	Yes	2
3. For the most difficult time you had swallowing food today (during the past 24 hours), did you have to do anything to make the food go down or to get relief?	No, it got better or cleared up on its own	0
	Yes, I had to drink liquid to get relief	1
	Yes, I had to cough and/or gag to get relief	2
	Yes, I had to vomit to get relief	3
	Yes, I had to seek medical attention to get relief	4
4. The following question concerns the amount of pain you have experienced when swallowing food. What was the worse pain you had while swallowing food over the past 24 hours? b	None, I had no pain	0
	Mild	1
	Moderate	2
	Severe	3
	Very Severe	4

a DSQ is modified with the addition of Question 1a when response to Question 1 is ‘No’.

b Question 4 does not assess dysphagia and is considered a standalone item to be evaluated as an exploratory outcome.

The DSQ score is calculated based on the daily responses to question 2 (frequency) and question 3 (severity) over a 14-day period using the formula from (Hudgens, 2017):

$$DSQ\ Score = \frac{(sum\ of\ points\ from\ questions\ 2\ and\ 3\ from\ daily\ DSQ\ diary) \times 14\ days}{number\ of\ diary\ days\ reported\ with\ non-missing\ data}$$

To calculate the DSQ score, a minimum of 8 diary entries (including days when patient responded ‘No’ to question 1) is required for each 14-day period to derive a standardized total score based on the cumulative scores through 14 days. If there are less than 8 diary entries for a 14-day period, the DSQ score is considered to be missing for that period. The primary analysis will be based on DSQ score calculated using this algorithm. If there are multiple diary entries on the same day, the first entry on that day will be used in calculating DSQ score for analysis. DSQ scores can theoretically range from 0 to 84, with a lower score indicating less-frequent or less-severe dysphagia.

As a sensitivity analysis, DSQ will be scored using an alternative algorithm that takes into account patient’s response to question 1a about reason for not eating solid food:

- If not eating solid food because of patient problems with swallowing solid food, a daily score of 6 will be assigned for that day for analysis but not for consideration of eligibility and used in the formula given above to calculate DSQ score over a 14-day period after randomization.
- If the patient responds to question 1a by indicating that he/she did not eat solid food since waking up in the morning because of something NOT related to their problems with swallowing solid food, no score will be assigned. Data for that day is considered to be missing for analysis but diary completion is considered compliant for that day.

Baseline DSQ scores will be calculated from daily responses recorded during the 14 days just prior to the first dose date. For example, if a patient is randomized and takes the first dose of study drug on Jan 15th, DSQ score will be calculated from daily responses recorded during Jan 1st through Jan 14th as baseline. DSQ scores at time points after baseline will be calculated for each 14-day period starting from the day of patient receiving their first dose of study drug (see detailed analysis time point window in Section 6.4).

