**DSQ total score:**

1. Tipping point analysis: To assess the robustness of analysis results under MNAR (missing not at random) assumption, a delta-adjusting pattern-mixture approach for tipping point analysis ([Ratitch, 2013](#)) will be conducted for the co-primary endpoints. The impact from missing data on comparisons in absolute change in DSQ score from baseline to week 24 between each Dupilumab group and placebo control group will be examined, by adjusting for stratification factors:
  - A sequence of analyses will be performed by adding a sequence of positive values in placebo group and subtracting a sequence of positive values in active treatment group for data imputation.
  - For each combination of adding and subtracting values, multiple imputed datasets will be generated and analyzed with the ANCOVA model. The results obtained from multiple imputed datasets will be combined using Rubin’s formula to generate statistical inference, i.e. p-value and LSmean of treatment difference between active treatment group and placebo group.
  - A “tipping point” will be identified while the result is no longer statistically significant (i.e. p-value >0.05).
2. A minimum of 4 diary entries (including days when patient responded ‘No’ to question 1) per week is required to derive a standardized total score for each 14-day period. The analysis method will be as same as the primary analysis.
3. DSQ will be scored using an alternative algorithm (detailed in section 4.4.1), i.e. assigning a DSQ daily score of 6 if patients do not eat solid food due to EoE. The analysis method will be as same as the primary analysis.

As in the primary analysis, DSQ data collected during the time when patient’s device did not direct DSQ questions properly will not be used in the above sensitivity analyses.

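### As worded, the alternative DSQ scoring covers only periods after randomization, which shifts within-arm change from baseline upward in that sensitivity analysis; the SAP should say that baseline is rescored too

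*SAP*

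**What the plan says.** Under the standard DSQ rule in SAP 4.4.1, a day without solid food carries no score: "Data for that day is considered to be missing for analysis but diary completion is considered compliant for that day". It leaves both the numerator and the denominator of the 14-day score, although it counts toward the minimum of 8 entries.

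The alternative algorithm uses question 1a, which asks why no solid food was eaten. If the reason was trouble swallowing, "a daily score of 6 will be assigned for that day for analysis but not for consideration of eligibility", and the score is "used in the formula given above to calculate DSQ score over a 14-day period after randomization". This is the only sentence that gives the alternative score a time scope.

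The paragraph that follows fixes the baseline window ("Baseline DSQ scores will be calculated from daily responses recorded during the 14 days just prior to the first dose date") and does not mention the 6-point rule.

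SAP 5.6.1, DSQ sensitivity analysis 3, says "DSQ will be scored using an alternative algorithm", refers back to 4.4.1, and uses the primary method, which is ANCOVA on change with baseline as covariate. It neither repeats the limit to periods after randomization nor says how baseline is scored.

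**The concern.** On the literal text, one kind of diary day is ignored before randomization and given the highest possible daily score afterwards. Week 24 is then on one scale and baseline on another, and the outcome is the difference between them. A patient who avoids food equally often at both visits appears to get worse. A patient who resumes eating loses the credit for it in the change score.

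This is the only planned DSQ analysis that uses question 1a. It is therefore the only check on how food avoidance affects a co-primary endpoint whose main score ignores avoidance days. What is at stake is whether its mean changes can be interpreted and, under some conditions, its precision.

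**Working it through.** **Scale.** Question 2 gives at most 2 points and question 3 at most 4 ("Yes, I had to seek medical attention to get relief"), so a day scores at most 2 + 4 = 6. Over 14 days that is 14 × 6 = 84, which reproduces the plan's figure: "DSQ scores can theoretically range from 0 to 84". An avoidance day under the alternative rule therefore sits at the daily ceiling.

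**One patient.** Take 14 complete baseline entries, k of them swallowing-related avoidance days, with mean score m on the other 14 − k days.

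- Standard score: m(14 − k) × 14/(14 − k) = 14m
- Alternative score: m(14 − k) + 6k
- Difference: k(6 − m)

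With N scored or avoidance days instead of 14, the difference is 14k(6 − m)/N. Week 24 is scored the same way under the literal and the consistent rule, so this baseline difference is the whole discrepancy in the change score. It is zero if k = 0 or m = 6, and never negative.

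Example: k = 4, with 25 points over 10 eating days (m = 2.5). The standard baseline is 25 × 14/10 = 35. The alternative baseline is (25 + 4 × 6) × 14/14 = 49.

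| Week 24 | Literal rule | Consistent rule |
|---|---|---|
| Unchanged | 35 to 49: +14 | 49 to 49: 0 |
| Solid food on all 14 days, still 2.5 per day | 35 to 35: 0 | 49 to 35: −14 |

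Other values of k(6 − m): m = 2 gives +4 (k = 1), +12 (k = 3) and +24 (k = 6); m = 4 with k = 2 gives +4. For comparison, SAP 2.3 assumes a treatment difference of −12.3 and reports a Part A placebo change of −9.6.

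**Whole arm.** The documents give no avoidance frequency, so everything from here rests on assumption. One simulation used 70 patients per arm, 3000 runs, eating-day means around 2.5, about 30% of patients prone to avoidance, and a tendency to avoid that carries over to week 24 unless treatment reduces it.

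| Scenario | Scoring | Placebo change | Active change | ANCOVA difference | SE |
|---|---|---|---|---|---|
| No effect | Literal | +3.65 | +3.65 | 0.00 | 1.66 |
| No effect | Consistent | −0.01 | +0.02 | +0.02 | 1.25 |
| Effect | Literal | +3.61 | −9.69 | −13.29 | 1.45 |
| Effect | Consistent | −0.01 | −13.31 | −13.30 | 1.21 |

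In the effect scenario both arms move by the same amount: 3.61 + 0.01 = 3.62 and −9.69 + 13.31 = 3.62. The contrast does not move. Rejection under no effect was 4.8% with literal scoring.

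Unchanged placebo patients with avoidance days shifted by about 12.6 on average, so the arm-level shift is roughly that figure times the affected share: 0.05 × 12.6 = 0.6 at 5%, and 12.6 at 100%.

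**Precision.** Across scenarios that varied the share of patients affected and how far avoidance persists, the ratio of residual variance (literal to consistent) ran from about 0.90 with no persistence to about 1.55 with full persistence. These are not bounds. The table implies (1.45/1.21)² = 1.44 and (1.66/1.25)² = 1.76, and other inputs can move the lower end as well.

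**The case against.** The strongest reply is that baseline rescoring was intended. DSQ eligibility is judged only on the diary before randomization (protocol 6.2.1, criteria 5 to 7). If the 6 could never reach that window, exempting eligibility would be redundant. SAP 5.6.1 also sets no time limit. This stands as a doubt about intent, and a reader should not infer that the SAP clearly means to leave baseline on the standard score. It does not rescue the text: the one sentence that gives a scope says after randomization, no sentence says baseline is rescored, and two programmers could derive different baselines.

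The second reply is that the inference is safe. That stands in full. A reader might infer that mixed scoring biases the treatment effect. It does not, because baseline precedes randomization and enters the ANCOVA as a covariate, so the adjusted contrast is the same for change as for the week-24 value.

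The third reply is that a loss of precision is not certain. This also stands. It requires baseline avoidance to predict week-24 avoidance, and a treatment that relieves dysphagia could break that link. The practical cost is also modest. For the planned −12.3 points with SD 15.0, a 43% higher variance lowers recomputed power from 99.8% to 98.1% at 70 per arm, and from 99.3% to 95.8% at 59 per arm (70 less 15% dropout).

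Finally, not every patient's change is shifted. Those with no baseline avoidance days, or with an eating-day mean of 6, are unaffected.

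**Conclusion.** The point holds as a wording defect in one sensitivity analysis, and it is minor. Under the literal rule, patients with baseline avoidance days and an eating-day mean below 6 have their change shifted upward by k(6 − m) with complete entries, so improvement is understated in both arms. That arithmetic needs no assumption.

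The arm-level size does: about +0.6 to +12.6 points as the affected share goes from 5% to 100%. Residual variance ran from about 10% lower to about 55% higher in the scenarios above, and a no-effect scenario gave 76% higher. All of these are illustrations, because the documents contain no avoidance data.

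The between-arm difference, the primary DSQ analysis (one algorithm throughout) and the testing hierarchy are untouched. The documents do not support describing this as a threat to the co-primary conclusion, or as a certain widening of the confidence interval.

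**What to change.** In SAP 4.4.1, delete the words that limit the score to periods after randomization. There and in 5.6.1 (DSQ sensitivity analysis 3), state that for this analysis the alternative algorithm applies to both the baseline and the post-baseline 14-day periods, and that eligibility alone keeps the standard score. The shift is then zero for an unchanged patient at every k and m.

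No new data are needed: the diary "will be completed by the patient daily using an eDiary from screening through end of study or ET visit", and protocol 8.2.2.2 says this is the modified version with the follow-up question. The cost is one sentence in two places and a derived baseline variable. The downside is that, if avoidance does not persist from baseline to week 24, the rescored baseline is a slightly poorer covariate and precision could be somewhat lower.

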#### 4.4.2. Secondary Efficacy Variable(s)

The key secondary endpoints for Part B are:

- Absolute change in EoE EREFS total score from baseline to week 24
- Percent change in peak esophageal intraepithelial eosinophil count (eos/hpf) from baseline to week 24
- Absolute change in EoEHSS mean grade score from baseline to week 24
- Absolute change in EoEHSS mean stage score from baseline to week 24

#### Eosinophilic Esophagitis-Endoscopic Reference Score (EoE EREFS)

EoE-EREFs is a validated scoring system for inflammatory and remodeling features of disease that are visible through endoscopy (Hirano, 2013). The proximal and distal esophageal regions will be scored separately. The score for each region is the sum of assigned scores for each of the 5 major features and ranges from 0 to 9. The total score (summing scores for the proximal and

distal regions) ranges from 0 to 18 and is the final score used for the analysis. If score is available only from 1 of the 2 regions, that available score will be used as total score. For example, if score is 8 from the proximal region and missing from the distal region, the total score will be 8.

The major esophageal features include:

- Edema (absent [0], present [1])
- Rings (absent [0], mild [1], moderate [2], severe [3])
- Exudates (absent [0], mild [1], severe [2])
- Furrows (absent [0], mild [1], severe [2])
- Stricture (absent [0], present [1])

The EoE-EREFS should be performed by the physician conducting the endoscopy procedure before biopsies. For Part B enrolled patients, EoE-EREFS will be performed by both the investigators who perform the endoscopies as well as a centralized reading center who will provide EoE-EREFS analysis and scoring from endoscopy imaging. The centralized reading will be used for analysis, if available. Given centralized readings were introduced for the first time for part B patients of this study, if the centralized reading is not possible (e.g. technical issues) for a given proportion of the FAS (e.g. >20% patients in FAS with either baseline or week 24 unavailable ([Dziura, 2013](#))), the EoE-EREFS performed by the investigator will be used for analysis, which will be consistent with part A.

In addition to the major features above, data for the following minor features will also be captured but not included in the EoE-EREFS scoring:

- Crepe paper esophagus (mucosal fragility or laceration upon passage of diagnostic endoscope): absent, present
- Narrow caliber esophagus (reduced luminal diameter of the majority of the tubular esophagus): absent, present
- Stricture diameter

Mucosal changes associated with gastroesophageal reflux disease will also be recorded (but not included in the EoE-EREFS scoring) using the Los Angeles classification system for erosions (No Erosions or Grade A, B, C, or D).

EoE-EREFS will be assessed by endoscopy at the second screening visit, week 24 and week 52 (EOS) or ET visits, and immediately prior to start of rescue medication or procedures. Patients undergoing endoscopy/biopsy prior to rescue will not undergo the scheduled endoscopy/biopsy at weeks 24 and 52.

#### Eosinophilic Esophagitis Histology Scoring System (EoEHSS)

The EoEHSS is a method for evaluating the grade and stage of multiple pathologic features in esophageal biopsies from EoE patients that extend observations beyond the presence of tissue eosinophils ([Collins, 2017](#)). EoEHSS evaluates eight features: eosinophil inflammation (EI), basal zone hyperplasia (BZH), eosinophil abscess (EA), eosinophil surface layering (SL), dilated intercellular spaces (DIS), surface epithelial alteration (SEA), dyskeratotic epithelial cells (DEC), and lamina propria fibrosis (LPF). Severity (grade) and extent (stage) of abnormalities will be

scored by a central, blinded pathologist for each feature using a 4-point scale (0 normal; 3 maximum change). The detailed scoring scheme for each feature is provided in Section 11.5.

The mean grade or mean stage score from EoEHSS for each biopsy is the ratio of the sum of the assigned scores for each feature evaluated divided by the maximum possible score for that biopsy (the maximum possible score for each biopsy is 24). For example, if all 8 features have maximum grade of 3 for a biopsy, the mean grade score will be  $24/24 = 1$ . If a feature is not evaluated, the maximum possible score is reduced by 3. Most maximum possible score reductions may occur because lamina propria is not present; if all other features are evaluable, the maximum possible score for a biopsy lacking lamina propria is reduced from 24 to 21 because 7 instead of 8 features were evaluated. Both mean grade and mean stage scores will be determined for biopsies from 3 esophageal regions (proximal, mid and distal). The mean grade and mean stage scores summed across the 3 regions is the final score used in the primary analysis of these endpoints. In the example given in the table below, the mean grade score is 0.33, 0.33, and 0.42 from the proximal, mid, and distal regions, respectively, and the final mean grade score is 1.08 ( $0.33 + 0.33 + 0.42$ ). If mean score is available from at least 1 of the 3 regions, the sum of available mean scores will be used as final mean score. For example, if the mean grade score is 0.33 and 0.33 from the proximal and mid regions but missing from distal region, the final mean grade score will be 0.66 ( $0.33+0.33$ ).

Feature	Esophageal region		
	Proximal	Mid	Distal
Eosinophilic inflammation (EI)	3	3	3
Basal zone hyperplasia (BZH)	2	3	3
Eosinophil abscess (EA)	2	2	3
Surface layering (SL)	0	0	0
Dilated intercellular spaces (DIS)	0	0	0
Surface epithelial alteration (SEA)	0	0	0
Dyskeratotic epithelial cells (DEC)	0	0	0
Lamina propria fibrosis (LPF)	missing	0	1
8-feature Mean Grade Score	$(3+2+2)/21=0.33$	$(3+3+2)/24=0.33$	$(3+3+3+1)/24=0.42$

Due to the anticipation that lamina propria may not be present in many biopsies, a total grade or total stage score by summing scores from the other 7 individual features will be calculated for an exploratory analysis. In the example given above, the total grade score excluding lamina propria is  $(3 + 2 + 2) + (3 + 3 + 2) + (3 + 3 + 3) = 24$ .

Esophageal biopsies will be obtained by endoscopy at the second screening visit (visit 2, day  $-21 \pm 7$ ), week 24 and week 52 (EOS) or ET visits, and immediately prior to the start of rescue medication or procedures. Patients undergoing endoscopy/biopsy prior to or due to the initiation of rescue will not undergo the scheduled endoscopy/biopsy at weeks 24 and 52.

The **other secondary** endpoints are:

- Proportion of patients achieving peak esophageal intraepithelial eosinophil count of  $<15$  eos/hpf at week 24
- Proportion of patients achieving peak esophageal intraepithelial eosinophil count of  $\leq 1$  eos/hpf at week 24

- Percent change in DSQ from baseline to week 24
- Normalized Enrichment Scores (NES) for the relative change from baseline to week 24 in the EoE diagnostic panel (EDP)
- NES of the relative change from baseline to week 24 in the type 2 inflammation signature
- Absolute change from baseline to week 24 in health-related QOL average score as measured by EoE Impact Questionnaire (EoE-IQ)
- Absolute change from baseline to week 24 in severity of EoE symptoms other than dysphagia and pain with swallowing as measured by EoE Symptom Questionnaire (EoE-SQ)
- Absolute change from baseline to week 24 in frequency of EoE symptoms other than dysphagia and pain with swallowing as measured by EoE Symptom Questionnaire (EoE-SQ)
- Proportion of patients who receive rescue medications or procedures during the 24-week placebo-controlled treatment period
- Absolute change from baseline to week 24 in esophageal distensibility plateau measured by endolumenal functional lumen imaging probe (EndoFLIP), if collected.
- All the above co-primary and secondary endpoints assessed at week 24 will be assessed at week 52 as additional secondary endpoints.
- All the above co-primary and secondary endpoints at week 24 and week 52 will be assessed in patients who have previously received swallowed topical corticosteroids as additional secondary endpoints.

